# 3.6 Study Termination/Subject Discontinuation or Withdrawal/Subject Revocation of Authorization

#### 3.6.1 Study Termination

3M or the Investigator has the right to terminate or suspend the study at any time for medical and/or administrative reasons. As far as possible, this should occur after mutual consultation.

## 3.6.2 Subject Discontinuation

The Investigator may discontinue individual subjects from the study at any time. Subjects may voluntarily withdraw from the study at any time. The Investigator will provide a written report on the appropriate CRF describing the date and reason for discontinuance.

A subject who is discontinued or voluntarily withdraws will not be replaced.

Page 12 of 36 Status: Release

Version: 3

Issue Date: 07/11/2019 03:08:44 PM CDT

#### [name]

## 3.6.3 Subject Revocation of Authorization to Use and Disclose PHI

In order to implement a valid revocation of authorization, the subject or their representative must make the request in writing to the Loma Linda University School of Dentistry, [name], [name], to the attention of the PI. The revocation cannot stop the use or disclosure of information that has been collected prior to the revocation, is needed to ensure complete and accurate study results, is required by law or government regulation (e.g., reporting adverse events, etc.). Revocation of an authorization may not be used to withhold normal medical care from the subject but will make the subject ineligible to receive the study treatment or care.

## 3.7 Investigational Material Accountability

3MTM always requires Investigators to maintain accountability and adequate inventory security of the experimental material at all times. The Investigator or designee will:

- Complete a Confirmation of Release and Receipt of Clinical Supplies form and maintain and account for inventory on the Investigational Material Disposition form.
- Keep experimental materials in a secure storage area, accessible only to authorized individuals.
- Dispense experimental material only to subjects properly enrolled into the study.
- Return all unused experimental materials to 3M at the end of the study or dispose of as agreed upon.

## 3.8 Randomization and Blinding

The cross-over order of treatments will be assigned using sealed randomization envelopes. Order assigned will be either A->B (AB) or B->A (BA). The Investigator or their designated staff member is responsible to assure that the study randomization is followed. Subjects randomized will have their data and records numbered with the assigned numbers 001 to 040. Study treatment materials will be labeled with the appropriate codes. The 3M study monitor must be notified within 24 hours of any emergency deviation from protocol related to randomization errors.

## 3.9 Source Data

Page 13 of 36 Status: Release

Version: 3

Issue Date: 07/11/2019 03:08:44 PM CDT

#### [name]

Data will be written on data collection sheets and then entered into the electronic data capture (eDC) database by research staff, the paper is then considered source data. The data entry should occur within a week of collection and copies of the data sheets should be sent to sponsor. Subject will be keeping a diary, this is considered source data, and will be returned to the research staff and transferred to the sponsor for data entry within a week of the return of the diary to the research staff. Completed paper data collection sheets and eCRFs will be reviewed by the site monitor to ensure accuracy and consistency of subject data. Any discrepancies found during CRF review are to be clarified by the Investigator or designee. Investigator must keep physical CRFs in the study subject binder for a minimum of 2 years after completion of the study.

#### 3.10 Protocol Modifications

#### 3.10.1 Protocol Amendments

The party initiating an amendment must confirm it clearly in writing using the Amendment/Administrative Revision form. It must be signed and dated by 3M and, in the case of a significant amendment, the Investigator. A significant amendment means one that affects the safety, rights or welfare of subjects, the scope of the investigation or the scientific quality of the study.

3M will notify the Investigator when a protocol amendment may be implemented.

#### 3.10.2 Protocol Deviations

A deviation is a departure from the protocol that will likely affect the safety, rights or welfare of subjects, the scope of the investigation or the scientific quality of the study.

A protocol deviation is only for an individual subject. Protocol deviations are documented on a Protocol Deviation Form or appropriate CRF.

Deviations that potentially affect 1) subject safety, rights or welfare, 2) data integrity or 3) compromise the statistical analysis of the study require immediate communication to 3M. The Investigator must contact the 3M study monitor within 24 hours of occurrence at the following [contact].

A Protocol Deviation Form must be completed by the Investigator and include the type of deviation and a description of the circumstances surrounding the deviation. A copy is sent to the 3M study monitor within 24 hours of identifying the occurrence.

Page 14 of 36 Status: Release

Version: 3

Issue Date: 07/11/2019 03:08:44 PM CDT

#### [name]

Deviations which are made to protect the life or physical well-being of a subject in an emergency must be reported to the IRB within 5 working days after 3M learns of the occurrence.

The major protocol deviations include subjects missing the primary endpoint visit for one or both treatment periods, subjects not taking product for one or more days, and subjects taking excluded medications (any non-study assigned dry mouth alleviating products).

## 3.11 Computerized Systems

All statistical analyses will be conducted using SAS software. Clindex will be used for electronic capture of study data. Electronic study documents will be stored in ENOVIA. Any additional computerized systems used in the conduct of this study will be identified in the study report.

## 4. Subject Selection

## 4.1 Subject Inclusion Criteria

## Screening – Start of Wash-In Visit

- Subject who is  $\ge 18$  years of age and complains of dry mouth
- Only 1 subject per household is allowed into study
- Subject with a Challacombe scale score of 1 or higher
- Subject agrees to refrain from eating spicy foods and foods containing garlic beginning 48-hours prior to all study visits
- Subject agrees to eat a meal prior to all study visits that include sample evaluation in the clinic
- Subject agrees to not eat, drink, chew tobacco, chew gum, smoke, brush or floss teeth for 2-hours prior to sample evaluation study visits
- Subject agree to not use any oral care products and any type of breath mint or lozenges for 2-hours prior to sample evaluation study visits
- Subject agrees to refrain from any food and liquid during the 5-hour study visits except for what is provided by the study research staff (e.g., water and treatments A and B during evaluation periods)
- Subject agrees to only use those clinical oral care supplies provided during the entire study
- Able to understand and willing to sign the Informed Consent Form

#### Water Only Evaluation Visit

- Subject has successfully completed a  $\geq$  2-day wash-in period
- Subject has Challacombe scale score of 1 or higher

Page 15 of 36 Status: Release

Version: 3

Issue Date: 07/11/2019 03:08:44 PM CDT

### [name]

- Subject has refrained from eating spicy foods and foods containing garlic beginning 48-hours prior to the sample evaluation visits
- Subject ate a meal prior to sample evaluation study visits
- Subject has not eaten, drank, chewed tobacco, chewed gum, smoked, brushed or flossed teeth for 2-hours prior to sample evaluation study visits
- Subject has not used any oral care products, any type of breath mint or lozenges for 2-hours prior to sample evaluation study visits
- Subject agrees to refrain from any food and liquid during the 5-hour study visits except for what is provided by the study research staff (e.g., water and treatments A and B during evaluation periods)
- Subject has used only those clinical oral care supplies provided during study

#### Baseline Period 1/Randomization Visit

- Subject has successfully completed a  $\geq$  2-day wash-in period
- Subject has a Challacombe Scale score of 1 or higher
- Subject has refrained from eating spicy foods and foods containing garlic beginning 48-hours prior to sample evaluation study visits
- Subject ate a meal prior to sample evaluation study visits
- Subject has not eaten, drank, chewed tobacco, chewed gum, smoked, brushed or flossed teeth for 2-hours prior to sample evaluation study visits
- Subject has not used any oral care products and any type of breath mint or lozenges for 2-hours prior to sample evaluation study visits
- Subject agrees to refrain from any food and liquid during the 5-hour study visits except for what is provided by the study research staff (e.g., water and treatments A and B during evaluation periods)
- Subject has used only those clinical oral care supplies provided during study
- 4.2 Subject Exclusion Criteria for Start of Wash-In, Water Only Evaluation and Baseline Period 1 (Randomization Visit)
  - Subject has active mouth sores (e.g., cold sores, cuts, burns, canker sores)
  - Subject has a life-threatening pathological condition
  - Subject is participating in another clinical trial at the time of the study
  - Subject has profound marginal periodontal disease (purulent exudate, tooth mobility, and/or extensive alveolar bone loss)
  - Medical and oral conditions that, in the investigator's judgment, may compromise the subject's safety or interfere with the conduct and outcome of the study
  - Difficult to be compliant with recalls, such as extensive travel commitments, lack of transportation etc.

#### 4.3 Subject Consent

The Principal Investigator or qualified Co-Investigators mentioned above are responsible for protecting patient confidentiality when discussing the study

Page 16 of 36 Status: Release

Version: 3

Issue Date: 07/11/2019 03:08:44 PM CDT

[name]

details. The potential subject will have as much time to make a decision about participation in the study as they need to ensure that they understand everything within the consent document. The Investigator must ensure that written informed consent to participate in the investigation is obtained before including any individual as a subject in the investigation. Written informed consent will be obtained after the aims, methods, anticipated benefits, and potential hazards are explained and each subject's questions have been answered. The Investigator must provide the prospective subject or their representative sufficient opportunity to consider whether or not to participate and minimize the possibility of coercion or undue influence. The process is designed to 1) give the subject all the information that they need, 2) ensure that the subject understands the information and 3) give the subject a chance to consider study participation. The process should permit the subject to ask questions and exchange information freely.

Specifically, the Investigator is to explain to each subject all elements of informed consent as specified in 21 CFR 50.25. After the explanation, the subject or representative will voluntarily sign and date the consent form if they wish to participate in the study. A copy of the consent form must be provided to the subject. A signed and dated copy of the consent form must be maintained in the Investigator study documentation file at all times. Consent and study participation, with date, must be documented in the patientrecord/chart.

Photographs will be taken of some of the subjects for non-diagnostic, publication and/or research development purposes. Of those subjects initially photographed, they will be followed throughout the study with photographs at each visit. For any extreme outcomes or outcome of interest to the investigator, subject photographs will be taken at any time throughout the study.

# 4.4 Subject Authorization for Use and Disclosure of Protected Health Information (PHI)

The Investigator must ensure that written authorization for use and disclosure of protected health information is obtained before including any individual as a subject in the investigation. Written authorization for use and disclosure of protected health information is combined with the consent form (e.g., compound authorization) and must be obtained by the Investigator prior to including any individual as a subject in the investigation.

Specifically, the Investigator is to explain to each subject all elements of authorization as specified in 45 CFR 164.508. After the explanation, the subject or representative must voluntarily sign and date the authorization form if they wish to participate in the study. A copy of the authorization form must be provided to the subject. A signed and dated copy of the authorization form must be maintained in the

Page 17 of 36 Status: Release

Version: 3

Issue Date: 07/11/2019 03:08:44 PM CDT

#### [name]

Investigator study documentation file at all times and may be placed in the patient's medical record.

An authorization form may be combined with a consent form (e.g., compound authorization) if required by the IRB. All required elements for both informed consent and authorization must be included in a compound authorization.

## 5. Treatment of Subjects

### 5.1 Treatment(s) to be Administered

## Visit 1 – Screening Visit/Start of Wash-In

- 1. The subject signs the study consent form and authorization form.
- 2. A study examiner will perform an oral exam and perform an assessment using the Challacombe-Scale to determine the severity level of dry mouth prior to any dosing. If the Challacombe score is 0, then the subject will not continue with study participation. If the Challacombe score is 1 or greater, subject will be enrolled.
- 3. Participants will be qualified using the inclusion/exclusion criteria set forth in this protocol.
- 4. Participant's medical history will be collected and recorded.
- 5. Subject will be instructed for how to perform at least a 2-day wash-in period.
- 6. Subject will be given clinical study oral care supplies.
- 7. The participant will be scheduled for a 5-hour appointment.

#### Visit 2 - Water Only Evaluation Visit

- 1. Confirm that subject still meets the inclusion/exclusion criteria set forth in this protocol.
- 2. Confirm there were no changes to medications.
- 3. A study examiner will perform an oral exam and perform an assessment using the Challacombe-Scale to determine the severity level of dry mouth prior to any dosing. If the Challacombe score is 0, then the subject will not continue

Page 18 of 36 Status: Release

Version: 3

Issue Date: 07/11/2019 03:08:44 PM CDT

#### [name]

with study participation. If the Challacombe score is 1 or greater, subject will complete water-only evaluation.

- 4. Subjects will not be allowed to eat or drink during the study visit except for when directed by study staff.
- 5. Subjects will be asked to complete a Dry Mouth Inventory (DMI) questionnaire to understand their opinion on their severity of dry mouth prior to water evaluation.
- 6. Subjects will be asked to complete a Visual Analog Scale (VAS) for mouth dryness for a baseline mouth dryness score prior to water evaluation.
- 7. Subjects will drink 15 ml of water in their mouth and swallow the water.
- 8. Subjects will be asked to answer 1 question regarding mouth dryness at 5-, 15-, 30-, 60-, 120-, and 240-minutes post single dose, using a Visual Analog Scale (VAS) assessment format and a Product Performance Attribute Question (PPAQ) format of none/no relief, not enough, some/good, very good, significant/excellent.
- 9. Also, subjects will be asked to answer an additional PPAQ on the secondary endpoints at 5-, 15-, 30-, 60-, 120-, and 240-minutes post single dose using a format- poor, fair, good, very good, excellent.
- 10. Subject will be instructed on restrictions during the study (e.g., no spicy foods, medicine, oral care products, gum, hard candy).
- 11. Subject will be scheduled for Baseline Period 1 visit. Note: Subjects will continue with water only wash-in requirements and be randomized on treatment day.

#### Visit 3 - Baseline Period 1

- 1. Confirm that subject still meet the inclusion/exclusion criteria set forth in this protocol.
- 2. Confirm there were no changes to medications.
- 3. A study examiner will perform an oral exam and perform an assessment using the Challacombe-Scale to determine the severity level of dry mouth prior to any dosing.

Page 19 of 36 Status: Release

Version: 3

Issue Date: 07/11/2019 03:08:44 PM CDT

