## 1. Background Information

1.1 Name, Description and Intended Use of the Experimental Material Xerostomia is a subjective sensation of dryness of the mouth. Dry mouth can be a symptom or a side effect of other conditions (e.g., diabetes, hypertension, Sjögren's syndrome, stroke). It is also a common side effect of many prescription and nonprescription drugs; including drugs used to treat hypertension, depression, anxiety, allergies, and colds (decongestants and antihistamines). Mouth dryness is commonly associated with oral symptoms such as taste disturbances, bad breath and painful mouth ulcers. Dry mouth can also affect oral functions such as speech, chewing, and swallowing. 1,2

Management includes symptomatic relief and prevention or correction of the sequelae of saliva hypofunction, and treatment of any underlying disease. Adequate hydration of the oral tissues (frequent sips of water) is the standard treatment of xerostomia. Several over-the-counter products (e.g., Biotène®) are also available for treating dry mouth symptoms; however, data collected during 3M-hosted focus groups and voice of customer activities indicated that there continues to be an increasing demand for effective dry-mouth relief products. For this reason, 3M's Oral Care Solutions Division plans to expand their prevention portfolio and has been developing an oral spray solution, which is intended to be used to relieve dry mouth symptoms in persons with Xerostomia.

The purpose of this clinical trial is to evaluate and validate the performance of the experimental mouth spray when used by persons with mild to severe dry mouth symptoms. This study is designed to gather data from these individuals regarding their opinions about the product's performance, mouth-feel qualities, and user's willingness to purchase the product when it becomes commercially available.

We hypothesize that the use of 3MTM Experimental Dry Mouth Moisturizing Spray will be non-inferior to Biotène (GSK) in alleviating dry mouth symptoms.

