#### [name]

- 4. Photographs may be taken of the subject's mouth for publication and/or research development purposes, no diagnosis, treatment or decisions will be made from the photographs.
- 5. A salivary flow test will be performed to determine if there is any hyposalivation.
- 6. Subjects will be asked to complete a Visual Analog Scale (VAS) for mouth dryness for a baseline mouth dryness score prior to dosing.
- 7. Sealed envelope is opened, and treatment order noted.
- 8. Subjects will not be allowed to eat or drink during the study visit except for when directed by study staff.
- 9. Subjects will self-administer 1-2 sprays into their mouth using the first sample assigned based on the randomization card.
- 10. Subjects will be asked to answer 1 question regarding mouth dryness at 5-, 15-, 30-, 60-, 120-, and 240-minutes post single dose, using a Visual Analog Scale (VAS) assessment format and a PPAQ format of none/no relief, not enough, some/good, very good, significant/excellent.
- 11. Also, subjects will be asked to answer an additional PPAQ on the secondary endpoints at 5-, 15-, 30-, 60-, 120-, and 240-minutes post single dose using a format- poor, fair, good, very good, excellent.
- 12. The subjects will be given a subject diary and instructed to record frequency of use, number of sprays, and any side effects and/or adverse events they experience while using their assigned study product.
- 13. Subjects will be instructed to use the product at home for 7 days. They will be scheduled to return to the clinic with their product container and subject diary. They will present for their follow-up appointment without having taken any of their sample product.
- 14. Subject will be instructed on restrictions during the study regarding food, medicine, oral care products, gum, hard candy.
- 15. Subjects will be instructed to use the product at home at least 1X/day.
- 16. Subjects will be instructed to call the clinic if they experience any adverse events.

Page 20 of 36 Status: Release

Version: 3

Issue Date: 07/11/2019 03:08:44 PM CDT

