#### 5.2 Medication(s)/Treatment(s) Permitted

Subjects will not be permitted to take new or change the dosing of medications at the time of randomization that will change their dry mouth conditions during the study. Otherwise, there will be no medication or treatment restrictions for the duration of the study. Subjects will be expected to only use dry mouth oral care relief and oral hygiene study products provided. In general, subjects will not be permitted to use non-study products that affect, exacerbate or alleviate their dry mouth symptoms other than the study products provided.

Page 23 of 36 Status: Release

Version: 3

Issue Date: 07/11/2019 03:08:44 PM CDT

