# 13. Appendices

# 13.1 Appendix A - Study Schedule

Visit	Screeni ng/Start of Wash- In	Water Only Evaluati on	Baseline Period 1	End of Treatme nt Period 1	Baseline Period 2	End of Treatme nt Period 2
Subject Meets Inclusion/Exclusion Criteria	X	X	X			
Subject Consented	X					
Subject Authorization	X					
Health History and Changes to Concomitant Medication	X	X	X	X	X	X
Give directions for wash-in/out ≥ 2-day period with water only	X			X		
Distribute oral care supplies (initially or as needed for on-going study)	X			X		
Subject Scheduled for Next Visit; give appropriate directions	X	X	X	X	X	
Subject Completed Wash-In ≥2-day period with Water Only		X			X	
Study Examiner Completes Oral Tissue Exam/Challacombe Scale	X	X	X	X	X	X
Water Only Evaluation – subject swallows 15 ml of water		X				
Subjects Randomized			X			
Salivary Flow Testing			X			
Photographs Taken (Selective)			X	X	X	X
Subjects Complete Dry Mouth Inventory (DMI) prior to dosing		X			X	
Subjects Complete Visual Analog Scale for Mouth Dryness, prior to dosing		X	X	X	X	X
1-2 sprays of sample self -dosed by subject in clinic			X		X	
Subjects Completes Assessment for (post single dose): VAS Form PPAQ form Dry Mouth Relief		X	X		X	
Subject Diary and take-home sample distributed, along with review of directions for take home use			X		X	
Subject Diary Collected				X		X
Experimental Sample Spray Bottle Weighed			X		X	
Experimental Sample Spray Bottle Collected and Weighed				X		X
Adverse Events Assessed		X	X	X	X	X
Usability and Sample Acceptance Questionnaires				X		X
Preference Questionnaire, Study Discontinuation or Completion to be completed at the final visit or at any time the subject is prematurely discontinuation.	uad.					X

to be completed at the final visit or at any time the subject is prematurely discontinued

An unscheduled visit may occur at any time during the study that may require a spray bottle replacement, protocol deviation, adverse event, or oral examination forms to be filled out

[figure not shown]

Care

Version: 3 Issue Date: 07/11/2019 03:08:44 PM CDT

Page 34 of 36 Status: Release

[name]

[figure not shown]

Page 35 of 36 Status: Release

Version: 3

Issue Date: 07/11/2019 03:08:44 PM CDT

[name]

Page 36 of 36 Status: Release

Version: 3

Issue Date: 07/11/2019 03:08:44 PM CDT

[name]

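### Visit 2 lists medicine among things not to be used during the study, which read literally contradicts section 5.2 and the protocol's own medication checks

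*Combined protocol and SAP*

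**What the plan says.** Section 5.1, Visit 2, step 10: "Subject will be instructed on restrictions during the study (e.g., no spicy foods, medicine, oral care products, gum, hard candy". A single negative governs the whole list of examples, and medicine is one of them.

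Section 5.1, Visit 3 step 14, Visit 4 step 7 and Visit 5 step 14 use a different form, in almost the same words each time: "Subject will be instructed on restrictions during the study regarding food, medicine, oral care products, gum, hard candy". This names medicine as a topic and does not state the restriction.

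Section 5.2 sets the medication rule in three parts:
- on changes: "Subjects will not be permitted to take new or change the dosing of medications at the time of randomization that will change their dry mouth" condition;
- on everything else: "Otherwise, there will be no medication or treatment restrictions for the duration of the study";
- on products: "subjects will not be permitted to use non-study products that affect, exacerbate or alleviate their dry mouth symptoms", other than those the study provides.

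Step 2 of Visit 2 reads "Confirm there were no changes to medications", and step 2 of Visits 3 to 6 says the same with trivial differences. Appendix A has a row "Health History and Changes to Concomitant Medication", marked at all six visits.

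Section 1.1 names common medicines as a cause of dry mouth: "including drugs used to treat hypertension, depression, anxiety, allergies, and colds (decongestants and antihistamines").

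**The concern.** Staff cannot deliver step 10 as written and also apply section 5.2. Stopping a regular drug is a change in medication, so a subject who took step 10 at face value would do what the step 2 checks are there to rule out.

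The population makes this more than an editorial matter. Subjects are enrolled because they complain of dry mouth, and section 1.1 says that drugs for hypertension, depression and anxiety are among the causes. Some subjects will plausibly be on such drugs, and an instruction that can be heard as a request to stop them is a safety matter first. It is a measurement matter second, because stopping a drying drug could alter the score that the trial compares.

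**Working it through.** No figure in the plan rests on this wording, so there is nothing to reproduce. The check compares the passages and then follows where a stop would enter the analyses.

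**Step 1: do the passages agree?**

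| Place | Content on medicine | Fits section 5.2? |
|---|---|---|
| 5.1, Visit 2 step 10 | In the list of things not to be used | No, if read literally |
| 5.1, Visits 2 to 6 step 2 | Confirm medication is unchanged | Yes |
| 5.1, Visits 3 to 5 instruction lines | Restrictions exist, content not stated | Yes, but uninformative |
| 4.1 and 4.2 | No criterion asks a subject to stop medicine or hold it stable | Yes |
| 3.10.2 | Excluded medications means non-study dry mouth products | Yes |
| Appendix A | Medication changes reviewed at all six visits | Yes |

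Only Visit 2 step 10 conflicts. The Visit 3 to 5 lines can be read as pointing to section 5.2, which does contain restrictions on medicine.

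**Step 2: what happens if a subject stops a drug after Visit 2?** Visit 3 step 2 should find it before randomization and before any spray. The check detects a stop but does not prevent it, and no step says what follows. Section 8.1 lists three grounds for per-protocol exclusion: a missing primary endpoint, product not taken for two or more days, and use of excluded dry mouth products. A changed medicine is not among them. It could reach the per-protocol decision only through the general provision for other deviations, which are judged blinded and documented before data lock.

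**Step 3: which comparison would be touched?** Let a fraction p of subjects stop a drying drug after Visit 2, shifting their VAS by d.
- *A versus water.* Water is always given on Day -1, before step 10, and A always afterwards. Without adjustment the mean difference shifts by p × d. The model in section 8.2.1 has no period term, so time cannot be separated from treatment. It does include the pre-dose VAS, which is recorded at Visits 2, 3 and 5. If each visit's own baseline is used, a fall in dryness before dosing is partly absorbed. Section 8.2.1 does not say plainly whether the baseline is visit-specific.
- *A versus B (primary).* Both periods follow step 10. If the shift lasts through both, then (A + d) − (B + d) = A − B, and it cancels within the subject. If it appears in one period only, it adds variability. The randomized order and the period term guard against a systematic shift.

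**Step 4: size.** The documents give neither p nor d, so p × d cannot be evaluated. For order AB, the shift would also have to develop in about one day, since Visit 3 is the day after the water test. For order BA, A is given on Day 9 or later, after the medication checks at Visits 3, 4 and 5.

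**The case against.** The strongest reply is that step 10 is shorthand. It is a list of examples in a staff procedure. The same negative covers oral care products, which the study itself supplies at Visit 1 and may top up at Visit 4, so the list cannot be a set of absolute bans. Section 3.10.2 gives excluded medications a narrow meaning, no eligibility criterion asks anyone to stop a drug, and medication is reviewed at every visit. The consent form and the instructions for use are not in the text available here, so what subjects actually read cannot be judged.

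Much of this stands. A reader might infer that the protocol tells subjects to give up prescribed drugs; the surrounding text makes that unlikely to be the intention. A reader might also infer that Visits 3 to 5 repeat the contradiction; their wording is compatible with section 5.2.

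The reply does not remove the need for an edit. For oral care products, section 4.1 states the exception plainly: the supplied products may be used. No visit step or criterion gives a matching exception for medicine. The narrow meaning in 3.10.2 sits in the deviation section, away from the instruction that staff pass on, and Visit 2 is the only visit step that says what the medicine restriction is.

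**Conclusion.** The inconsistency is real, is confined to one line, and is minor. Read literally, Visit 2 step 10 contradicts section 5.2 and the unchanged-medication checks. The Visit 3 to 5 lines do not contradict section 5.2 but leave the restriction unstated. The case for correcting it rests mainly on subject safety.

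A reader might go further and conclude that the instruction biases the trial in favour of the spray. The documents do not support that. They give no rate of stopping and no effect of stopping. The comparison most exposed is the non-randomized one with water, where the baseline covariate would take up part of any shift if baselines are visit-specific. In the primary A-B comparison a sustained stop largely cancels. No bias figure should be attached to this point.

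The conclusion assumes that staff might convey step 10 as written. If they already convey section 5.2 instead, there is no effect on subjects and only the text needs correcting.

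**What to change.** 1. Reconcile Visit 2 step 10 with section 5.2, so that staff have one rule on medicine to give. Which rule applies is for the sponsor and the investigator to decide.
2. Have the instruction lines at Visits 3, 4 and 5 refer to that same rule, and check that any subject-facing material agrees.
3. Record the date of any medication started, stopped or changed that is found at the existing visit checks, and bring those subjects to the blinded per-protocol review in section 8.1 before data lock.

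The cost is an edit to four instruction lines and a date beside information already being collected. Visits, sample size and the primary model stay as they are. Because the wording bears on subject safety, section 3.10.1 may class the edit as a significant amendment, which the investigator would also sign.
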